Maintenance	# of hospitals (of 3) conducting microdosing 3m after grant	Interviews with providers about current practices

perceived benefits), and implementation processes (e.g., protocol adaptation). Questions will identify barriers, such as provider stigma about OUD, and facilitators, such as leadership endorsement of protocols.

D.3.5 Analytic Plan: Interviews will be audio-recorded, digitally stored on an encrypted password protected computer, and professionally transcribed without participant identifiers. We will use thematic analysis to identify key themes relating to BUP initiation and implementation. *Initial review of data:* In an iterative process, [name] and team will read all interview transcripts and record concepts that emerge upon repeated readings.

Developing a coding scheme: The coding scheme will be based on the interview data and the goals of this project. The codebook will be discussed and agreed upon by the entire research team. Any necessary changes will be made by consensus. *Coding:* Using the codebook, two research team members will code data independently. The research team will meet, discuss codes, and, if there are any inconsistencies, will come to a consensus agreement as to application of codes for each transcript. Using Dedoose software (SocioCultural Research Consultants, Los Angeles CA), codes will be applied to the dataset and data will be organized by code. *Sorting:* After data are sorted and main themes are identified, the research team will meet again to ensure that all concepts are properly represented and that thematic saturation has occurred. *Member-checking:* Identified themes will be presented to study participants to elicit interpretation and additional insight.

D.4 Aim 3b: To calculate costs and examine cost-effectiveness of the BUP microdosing protocol

H₅: Compared with TAU, microdosing will be cost-effective from a societal and a health sector perspective. Following recommendations of the Second Panel on Cost-effectiveness in Health and Medicine,¹³⁴ we will take two reference case perspectives: a health care sector perspective and a societal perspective, over a 6-month time horizon. We will use quality-adjusted life years (QALYs), a key indicator for patient wellbeing, as the effectiveness measure.¹³⁴ Health Related Quality of Life (HRQoL) at discrete time points will be measured using a utility score resulting from the PROMIS-Preference (PROPr) system.¹²³

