For each reference case perspective, to estimate the incremental HRQoL and costs associated with the intervention – BUP microdosing vs. TAU – we will use intent-to-treat design and estimate a mixed Generalized Linear Model of the HRQoL/costs at the patient-level and at each assessment point as a function of patient assignment to microdosing (vs TAU), site fixed effects, and patient characteristics bearing implications for the outcomes but possibly not balanced at baseline, with random effects at patient and site levels.¹⁴⁶ The method of recycled predictions will be used to obtain predicted mean values for HRQoL and each cost category, by study arm. QALYs gained will be estimated using the area under the curve methodology.¹⁴⁷⁻¹⁴⁹ Predicted costs from different cost categories will be summed and tested according to relevant perspectives.¹⁴⁹ We will derive predicted *incremental* costs for intervention vs TAU for each individual patient based on the estimated models.

Cost-effectiveness analysis (CEA) will estimate an incremental cost-effectiveness ratio (ICER) associated with BUP microdosing vs. TAU. The ICER will be calculated by dividing (mean) incremental cost associated with microdosing vs TAU by (mean) incremental effectiveness. Sampling uncertainty in the estimated ICER will be taken into account by bootstrapping the study sample of the individual-level incremental cost and incremental effectiveness estimates and deriving non-parametric confidence intervals. We will further construct ICER acceptability curves for both reference case perspectives. Acceptability curves display the probability that an ICER would fall below a given willingness to pay for an incremental unit of the desired outcome and thus be considered a good value (that is, cost-effective).^{150,151}

D.5 Design considerations and limitations:

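### The ICER bootstrap is worded as resampling model-predicted patient increments, with no refit stated; with the models held fixed it would omit the error in the arm effect

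*Combined protocol and SAP*

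**What the plan says.** Section D.4 (Aim 3b) examines H5, that microdosing is cost-effective, from "a health care sector perspective and a societal perspective, over a 6-month time horizon". After Table E-7 the analysis runs in this order.

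1. A mixed generalised linear model is fitted to quality of life and to costs "at the patient-level and at each assessment point as a function of patient assignment to microdosing", with site and patient characteristics as further terms and "with random effects at patient and site levels". No arm interaction is listed, and no distribution family or link is given.
2. Recycled predictions give means by arm, and QALYs are areas under the curve. For costs, "Predicted costs from different cost categories will be summed and tested according to relevant perspectives".
3. Increments are then derived from the fits. The plan speaks of predicted incremental "costs for intervention vs TAU for each individual patient based on the estimated models".
4. The ICER is the ratio of mean increments. The sentence on its uncertainty opens with the purpose, "Sampling uncertainty in the estimated ICER will be taken into account by", and the means it then names is "bootstrapping the study sample of the individual-level incremental cost and incremental effectiveness estimates and deriving non-parametric confidence intervals".
5. Curves are drawn for both perspectives. "Acceptability curves display the probability that an ICER would fall below a given willingness to pay".

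The plan does not say whether steps 1 to 3 are repeated in each bootstrap sample.

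**The concern.** In a parallel-arm trial nobody is observed under both treatments. A patient's increment is therefore the model's prediction under microdosing minus its prediction under TAU. The plan says this outright for costs; for effectiveness it is implied by the bootstrap sentence. If those predictions are resampled while the fitted models stay as they are, the estimated arm effect is the same number in every replicate. The main source of uncertainty in an ICER, the error in that arm effect, never enters.

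The interval and the curves are how the plan expresses confidence in H5. An interval that is far too narrow, and a curve that jumps from near 0 to near 1 (or the reverse) around the point ICER, would make a chance difference look almost certain at most thresholds. The separate test of summed costs protects a statement about costs alone. It does not repair the ICER interval or the curves.

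**Working it through.** **No figure to reproduce.** The plan gives no interval, variance, family, link or threshold for this analysis. The check is therefore algebra, then simulation under stated assumptions.

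**From the plan.** 270 patients, 1:1 (D.2.1); arm, site and patient characteristics in the model, with patient and site random effects (D.4); visits at 1, 3 and 6 months; 6-month horizon.

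**Step 1, identity link, no arm interaction.** The predicted increment at a visit is the arm coefficient b for every patient, and patient random effects cancel in the difference. A QALY area is a fixed weighted sum of such coefficients. Every patient has the same increment, so every resample has the same mean and the width is zero.

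**Step 2, log link.** Increment for patient i = m_i × (exp(b) − 1), where m_i is the predicted mean under TAU. With b fixed, only the mix of m_i varies. The relative standard error (SE) of the mean increment is CV(m)/√n, with CV(m) = √(exp(v) − 1) and v the variance of log m.

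Assume two covariates contributing 0.25² × 1.16, site effects contributing 0.1² × 2/3, and a patient random effect of SD s kept in the prediction:

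- s = 0: v = 0.0725 + 0.0067 = 0.0792; CV = 0.287; 0.287/√270 = 1.7%.
- s = 0.4: 3.2%.
- s = 1.0: 8.5%.

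For comparison, refitting with an assumed cost CV of 1.2 and a 10% cost difference gives an SE of the log ratio of 1.2 × √(2/135) = 0.146. Relative to log(1.1) = 0.0953 that is about 153%.

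**Step 3, one simulated trial.** Assumed: mean cost 20,000, cost CV 1.2, cost ratio 1.10, QALY difference 0.02, residual QALY SD 0.10, gamma log-link costs, identity-link QALYs. The trial was chosen so that its estimates lie near those values: incremental cost 2,195, incremental QALYs 0.0156, ICER about 140,600. The curve is the share of replicates with positive net benefit.

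| | Models fixed | Refitted |
|---|---|---|
| SE, incremental cost | 41 | 2,970 |
| 95% interval, incremental cost | 2,124 to 2,280 | −3,378 to 8,353 |
| 95% interval, incremental QALYs | 0.0156 to 0.0156 | −0.0105 to 0.0404 |
| Curve at 125,000 per QALY | 0.00 | 0.45 |
| Curve at 150,000 per QALY | 0.999 | 0.49 |

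The cost-interval widths are 156 and 11,731, a ratio of 1.3%. Across four such settings the refitted SE of incremental cost was 25 to 148 times the fixed-model one. Over 400 simulated trials in each of two settings, nominal 95% intervals for incremental cost covered the truth in 1% and 6% of trials with models fixed, against 96% and 91.5% with refitting.

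**Step 4, a second simulation with visit-level costs.** Ten scenarios, 200 trials each with 200 bootstraps: three sites, gamma costs with a patient random intercept (log SD 0.6), TAU 6-month mean about 20,000, trapezoid QALYs, no missing data. Marginal fits replaced mixed fits for speed. Monte Carlo error is about 2 to 3 points.

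| | Models fixed | Refitted |
|---|---|---|
| Cost-interval width, % of refitted | 1.2 to 13.5 | 100 |
| Cost coverage, %, eight scenarios with a true cost difference | 1.5 to 19.5 | 90.0 to 95.5 |
| Share of thresholds from 0 to 200,000 dollars with curve ≤2.5% or ≥97.5% | 89.5% to 99.8% | 7.0% to 70.7% |
| Curve that extreme at 50,000, 100,000 or 150,000 dollars when neither cost nor QALYs truly differ, % of trials | 93 to 100 | 6.5 to 10 |

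The QALY-interval width was 0% of the refitted width without an arm interaction, and about 4% with an arm by baseline-utility interaction.

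**Side check, recall windows.** D.4.1 asks about health care use and crime over three months at each visit. The follow-up windows are months −2 to 1, 0 to 3 and 3 to 6: 9 months of recall for a 6-month horizon. Two thirds of the month-1 window precedes randomisation. With equal rates before and after, a true 20% reduction in month 1 shows as 20%/3 = 6.7% in that report.

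**The case against.** The strongest reply is that the plan is silent on refitting; it does not say the models are frozen. The sentence opens with the purpose of capturing sampling uncertainty and speaks of bootstrapping the study sample. Resampling patients and refitting is a fair reading, and the only one that meets that purpose. An analyst would probably also notice a zero-width QALY interval. This stands. A reader might infer that the plan prescribes a fixed-model bootstrap; the text does not go that far. What remains is that the object it names for resampling is the set of patient-level estimates, and nothing elsewhere corrects that.

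A second tempting reading is that the fixed-model interval reflects only the covariate mix. That is exact only for fixed-effect predictions without arm interactions. The plan specifies patient random effects, and if these stay in log-link predictions, or arm interactions are added, the spread is somewhat larger. Neither simulation fitted patient random effects; Step 2 bounds their contribution. The error in the arm effect is still missing.

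Third, the percentages are scenario-built, and refitting is not perfect either: its coverage fell to about 90% in places. In one scenario with a 20% cost saving, the refitted curve was already extreme at 70.7% of thresholds, so practical harm varies.

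On recall, a reader might infer that month 1 is counted twice or that the comparison is biased. Double counting would need the visits to be summed directly, which the plan does not say. Earlier use is balanced in expectation, so the effect is noise and dilution. A secondary claims analysis for 40-50% of patients avoids recall for health care costs, though not for crime.

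**Conclusion.** The point holds as a conditional one. Followed literally, with fitted models held fixed, the procedure leaves out the error in the arm effect, and the interval and acceptability curves are far too confident. The direction follows from the algebra for an identity or log link. The size, a fixed-model cost interval of roughly 1% to 14% of the refitted width in the scenarios tried, rests on assumed variances, family, link and covariate spread, because the plan gives none.

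If refitting is intended, the analysis is sound in this respect and only the wording is at fault. The plan states no decision rule or threshold for H5, so it cannot be said that a formal test would fail; the harm is to how strongly the result would be read. The matter should be settled before analysis. The recall overlap is a side clarification only.

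**What to change.** State in D.4 that patients are resampled within arm, with all their visits and their paired costs and quality-of-life data kept together. State that in every replicate the cost and quality-of-life models, recycled predictions, QALY areas and cost sums are re-estimated, and that the interval and acceptability curves are formed from the replicate mean increments. Resampling within site as well is optional, and gives small strata if one hospital enrols few patients. If missing cost or quality-of-life data are imputed, say how imputation and bootstrap are combined; the imputation text in D.2.11 sits under Aims 1 and 2.

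This costs a few sentences and computing time, with no change to data collection. Intervals will be wider and curves flatter, so H5 may look less clear-cut.

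Side clarification: build the 6-month totals for health care use and crime from the month-3 and month-6 reports, which cover months 0 to 6 once. The month-1 report is then not used directly, which loses some information on people lost before month 3. At the 84% retention precedent in D.2.6, 270 × 0.16 = about 43 people would be lost by month 6. The month-1 report can be kept to help impute a missing month-3 report.

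### The acceptability curve is described as the chance that the ICER is below willingness to pay, with no condition on the sign of the QALY difference; applied literally, it misclassifies replicates with fewer QALYs.

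*Combined protocol and SAP*

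**What the plan says.** All of this is in section D.4 (Aim 3b) of the combined protocol and SAP.

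- Effectiveness measure and horizon, in the opening text under H5: "We will use quality-adjusted life years (QALYs), a key indicator for patient wellbeing, as the effectiveness measure", assessed "over a 6-month time horizon".
- The ratio, in the cost-effectiveness analysis paragraph: "The ICER will be calculated by dividing (mean) incremental cost associated with microdosing vs TAU by (mean) incremental effectiveness".
- Uncertainty, in the same paragraph: it is to be handled by "bootstrapping the study sample of the individual-level incremental cost and incremental effectiveness estimates". From these resamples the team plans on "deriving non-parametric confidence intervals". No interval method is named.
- The curve, at the end of that paragraph, is said to show "the probability that an ICER would fall below a given willingness to pay". A ratio on that side of the threshold is then read with no further condition: "and thus be considered a good value (that is, cost-effective".

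The last item is the only definition of the curve in the documents. The section has no rule for negative ratios, no treatment of a QALY difference at or near zero, no net-benefit form and no list of thresholds.

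**The concern.** Comparing a cost-effectiveness ratio with a threshold gives the right decision only when the QALY difference is positive. If microdosing costs more and yields fewer QALYs in a replicate, the ratio is negative and lies below every positive threshold, so the worst possible result is scored as good value. If it costs less and yields fewer QALYs, the inequality should be reversed, because a low ratio then means that little money is saved per QALY lost.

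The plan itself allows for results of this kind. Section B.9 accepts that microdosing might lengthen the hospital stay, and Table E-7 costs the intervention by hospital night, so a higher cost with an uncertain QALY gain is possible. At stake is the probability of cost-effectiveness that would be reported in support of H5.

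**Working it through.** **1. The plan's own figure.** Section D.4 gives no expected ICER, QALY difference, variance or interval, so there is nothing to reproduce.

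**2. Sign check, which needs no assumption about the trial.** Let dE and dC be the incremental QALYs and cost, and let K be the threshold. Net monetary benefit is NMB = K × dE − dC, and the intervention is worth adopting at K when NMB > 0. Dividing dC < K × dE by dE gives ICER < K only if dE > 0; if dE < 0 the inequality reverses. With K = $100,000:

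| dE | dC | ICER | ICER < K? | NMB |
|---|---|---|---|---|
| +0.01 | +$300 | $30,000 | yes | +$700 |
| +0.01 | −$300 | −$30,000 | yes | +$1,300 |
| −0.01 | +$300 | −$30,000 | yes | −$1,300 |
| −0.01 | −$300 | $30,000 | yes | −$700 |
| −0.01 | −$3,000 | $300,000 | no | +$2,000 |

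The first two rows are right and the last three are wrong.

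**3. How often a replicate has dE ≤ 0.** With 135 per arm (D.2.12) and a standardized QALY effect d, the standard error of d is √(2/135) = 0.122, and P(dE ≤ 0) = Φ(−d/0.122). This gives 34% at d = 0.05, 21% at 0.10, 5% at 0.20 and 0.3% at 0.34. These values of d are assumed. The top one is the detectable effect that D.2.12 gives for pain, not an expected QALY effect.

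**4. Size of the error in the curve.** All inputs are assumed:

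- SE of dE is 0.01. A utility SD of 0.15 to 0.25, averaged over half a year, gives 0.5 × SD × 0.122 = 0.009 to 0.015.
- SE of dC is $3,000, K is $100,000, and dE and dC are normal and uncorrelated.

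Literal rule: P(dE > 0 and dC < K × dE) + P(dE < 0 and dC > K × dE).

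Net benefit, for mean gain g and mean cost c: Φ((K × g − c)/√((K × 0.01)² + 3,000²)), where the denominator is √(1,000² + 3,000²) = 3,162.

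| Mean gain (in SE) | Mean cost | (K × g − c)/3,162 | Literal rule | Net benefit |
|---|---|---|---|---|
| 0.005 (0.5) | +$1,500 | −0.316 | 54% | 38% |
| 0 (0) | +$3,000 | −0.949 | 56% | 17% |
| 0.01 (1) | −$1,500 | 0.791 | 75% | 79% |
| 0.02 (2) | +$1,500 | 0.158 | 57% | 56% |
| 0.03 (3) | +$1,500 | 0.474 | 68% | 68% |

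In the first row, replicates with dE > 0 contribute 30.1% under either rule. Among replicates with dE < 0 the literal rule accepts a further 23.4%, of which Φ(−0.5) × Φ(0.5) = 0.309 × 0.691 = 21.3% are dominated. Net benefit accepts 7.4%. The totals are 53.6% and 37.6%.

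**5. The interval.** In the first scenario the ratio of means is $1,500/0.005 = $300,000 per QALY. If the 2.5 and 97.5 percentiles of the replicate ratios were used, the limits would be about −$3.7 million and +$3.8 million. Each tail mixes replicates of opposite meaning: a large negative ratio may be a saving with a small QALY gain or a cost with a small QALY loss.

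**The case against.** The strongest reply is that the sentence explains what acceptability curves are, with textbook citations, and is not a programming rule; a health economist may well use net benefit anyway. That stands as far as it goes: the documents do not show that dominated replicates will be counted as good value, only that the one definition given would do so and that nothing beside it prevents this.

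A reader might infer several stronger things that the documents do not support.

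- *That a percentile interval of the ICER is planned and is meaningless.* The text says only that the intervals are non-parametric. The criticism of a percentile interval is conditional on that choice and on a QALY difference not clearly away from zero.
- *That H5 will be decided on this curve.* No threshold, probability cut-off or decision rule is set for H5, and the ICER and its interval come first.
- *That the 6-month horizon itself makes many replicates cross into QALY loss.* A constant utility difference u becomes 0.5 × u QALYs, but its standard error is halved too. Crossing depends on their ratio, which is unchanged.
- *That the tabulated percentages are what this trial would report.* They assume replicates that carry full two-sample uncertainty. The plan resamples model-predicted individual increments; if the models are not refitted in each resample, estimation uncertainty is left out and replicates may seldom cross quadrants. That is a separate question, and it does not make the definition correct.

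It is also fair that the scenarios with large gaps all have gains of one standard error or less. From about two standard errors upwards the two rules nearly agree.

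**Conclusion.** The point holds in conditional form. The sign error in the definition is a matter of algebra and rests on no assumption about the trial. Its effect on the result does depend on assumptions, since the documents supply no QALY or cost difference or variance. Under those used here the curve is overstated by 16 percentage points (54% against 38%, which also moves it across 50%) or by 39 points (56% against 17%), and understated by 4 points in the cost-saving case. The gap is about 1 point at a gain of two standard errors and negligible at three. Two standard errors is d = 2 × 0.122 = 0.24 at 135 per arm.

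The point concerns Aim 3b (H5) only. It does not touch the primary outcome or the sample size. It is worth correcting because the better definition costs almost nothing.

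**What to change.** In the cost-effectiveness analysis paragraph of D.4:

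- Define the acceptability curve, for each perspective, as the share of bootstrap replicates in which threshold × incremental QALY − incremental cost is greater than zero, over a threshold range stated in advance.
- Report the net monetary benefit with its bootstrap confidence interval at those stated thresholds, together with the cost-effectiveness plane, so that replicates with a QALY loss are visible.
- Name the method for any ICER interval, and give that interval only when the QALY difference is clearly away from zero.

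The cost is a sentence or two in the plan. The same replicates are used, no further data are collected, and the change can be made before analysis.
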